Secondary Objectives	Characterize participant retention, immune biomarkers, treatment satisfaction, and safety and tolerability at 6 and 12 months after transitioning to ofatumumab.
Study design	This is a single-arm, multicenter, prospective study in approximately 100 participants who are transitioning from aCD20 therapy to ofatumumab. This study consists of three parts: The 28 day screening period, the 12 month treatment period, plus a 30-day telephone safety follow-up and if required every 3 month post treatment safety follow-up visits until either another therapy is initiated or B cells are repleted, defined as a B cell concentration greater than the individual participant's baseline value prior to starting the IV anti-CD20 mAb or greater than the lower limit of normal. The minimum duration of the study for participants that complete the study is 14 months.
Population	Adult (ages 18 to 60) relapsing multiple sclerosis participants
Key Inclusion criteria	Participants eligible for inclusion in this study must meet all of the following criteria: 
 1. Written informed consent must be obtained before any assessment is performed. 2. Male or female participants aged 18 to 60 years (inclusive) at screening. 3. Diagnosis of relapsing MS (RMS) according to the 2017 Revised McDonald criteria including CIS, RRMS or SPMS with disease activity as defined by Lublin et al. 2014. 4. Disability status at Screening with an EDSS score of 0 to 5.5 (inclusive).

[figure not shown]

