2.2 Secondary estimands

Not applicable

3 Study design

This is a single-arm, multi-center, prospective, study in approximately 100 participants with relapsing multiple sclerosis who have been previously treated with aCD20 mAb therapy and have received at least 2 consecutive courses of intravenously administered ocrelizumab or rituximab every 6 months and the last dose is within 4 to 9 months before Baseline/Day 1. In this study, participants may enroll only if discontinuing aCD20 therapy for reasons other than lack of efficacy or due to certain treatment-emergent adverse events. Reasons for switching may include but are not limited to physician/participant preference, access to commercial drug (e.g. insurance coverage issues) or for other logistical reasons (such as geographical relocation, travel, etc.) A total of approximately 100 eligible participants will receive open label ofatumumab 20 mg subcutaneous once monthly for 12 months following initial loading regimen of 20 mg subcutaneous doses on Days 1, 7 and 14.

Assessments will be done per the assessment schedules ([Table 8-1](#) and [Table 8-2](#)).

For participants who discontinue study treatment prematurely for any reason before the end of the treatment phase, an End of Study visit must be performed within 7 days of study discontinuation.

Upon completing the study, participants may continue ofatumumab therapy on commercial drug.

Safety follow-up:

[figure not shown]
- The Safety follow-up (FU) period will be applicable for the following participants:
 - participants who complete the Treatment period on the study drug and do not continue on any MS DMT.
 - participants who prematurely discontinue study drug and do not continue on any MS DMT.
- All Safety FU visits must be scheduled relative to the End of Study (EOS) Visit.

Participants that do not continue into the ofatumumab commercial patient services hub within one month of the EOS Visit or that do not switch to another therapy, must continue into the safety FU phase, consisting of every 3 month visits including B cell monitoring until they are able to start on commercial ofatumumab or until they switch to another therapy or until their B cells are repleted defined as a B cell concentration greater than the individual participant's baseline value prior to starting the IV anti-CD20 mAb or greater than the lower limit of normal. All participants will have a safety follow-up phone call at 30 days post study.

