A shortened follow-up time is acceptable if participants select different treatment during this period or show earlier repletion. If participants are not fully repleted by the 6 month post-trial safety follow-up visit, further follow up visits at a 3 monthly frequency are recommended until full repletion has occurred. ([Table 8-2](#))

For participants completing the trial, the total duration of the trial will be a minimum of 14 months. This accounts for the 28 day screening period, the 12 month treatment period, and a 30 day telephone safety follow-up. Safety follow-up may be longer if the participant has not switched to another therapy post-trial and B cell repletion has not occurred.

Figure 3-1 Study design

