Participants who prematurely discontinue the study for any reason should be scheduled for the EOS visit within 7 days and then enter the Safety Follow-up period according to the schedule in Table 8-2. At this final visit, all dispensed investigational product should be reconciled, and the adverse event and concomitant medications should be recorded on the CRF.

Table 8-1 Assessment Schedule

Period ¹	Screening / BSL		Treatment Period													End of Treatment /Study	Follow-up	Unplanned
	Screening	BSL V1	V2	V3	V4	V5	V6	V7	V8	V9	V10	V11	V12	V13	V14	EOT/EOS V15 ⁵	Safety	Unscheduled Visit
Visit Name	-28 Days	D1	D7	D14	M1	M2	M3	M4	M5	M6	M7	M8	M9	M10	M11	M12	30-Day Tel.	UPV
Visit Day (D)/Month (M)			±1d	±1d	±3d	±3d	±3d	±3d	±3d	±3d	±3d	±3d	±3d	±3d	±3d	±3d	±7d	
Visit Window Days (d)																		
Obtain Informed Consent	X																	
Inclusion/exclusion criteria	X	X ¹²																
Demography	X																	
Medical History	X																	
MS disease/Treatment History ⁶	X																	
Historical IgM and IgG	X ²⁵																	
Physical Exam	S	S ¹²			S					S						S		S
Vital Signs	X	X ^{12,13}			X ¹³					X ¹³						X ¹³		X
Height	X																	
Weight	X	X ¹²			X					X						X		
ECG	X	X ³														X		X ²⁴
MRI ⁹	X ¹⁰									X						X ¹¹		
Chemistry ¹²	X ¹⁶	X ¹²			X					X						X		X

Period ¹	Screening / BSL		Treatment Period													End of Treatment /Study	Follow-up	Unplanned
Visit Name	Screening	BSL V1	V2	V3	V4	V5	V6	V7	V8	V9	V10	V11	V12	V13	V14	EOT/EOS V15 ⁵	Safety	Unscheduled Visit
Visit Day (D)/Month (M)	-28 Days	D1	D7	D14	M1	M2	M3	M4	M5	M6	M7	M8	M9	M10	M11	M12	30-Day Tel.	UPV
Visit Window Days (d)			±1d	±1d	±3d	±3d	±3d	±3d	±3d	±3d	±3d	±3d	±3d	±3d	±3d	±3d	±7d	
Hematology	X ¹⁶	X ¹²			X					X						X		X
Sample for CD19+ B-cells and CD3+CD20+ T-cells	X ¹⁶	X ¹²			X					X						X		X
Total IgG and IgM levels	X ¹⁶	X			X					X						X		X
Hepatitis A, B, C and E	S ¹⁶																	
Syphilis	S ¹⁶																	
Tuberculosis	S ¹⁶																	
HIV	S ¹⁶																	
Pregnancy Test (serum)	S ¹⁶				S					S						S		S
Pregnancy Test (urine) ¹⁷		S ¹²				S	S	S	S		S	S	S	S	S			S
Dipstick urinalysis ²¹	X	X			X					X						X		X
IRT Call	S	S ¹²			S					S						S		

Period ¹	Screening / BSL		Treatment Period													End of Treatment /Study	Follow-up	Unplanned
	Visit Name	Screening	BSL V1	V2	V3	V4	V5	V6	V7	V8	V9	V10	V11	V12	V13			
Visit Day (D)/Month (M)	-28 Days	D1	D7	D14	M1	M2	M3	M4	M5	M6	M7	M8	M9	M10	M11	M12	30-Day Tel.	UPV

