
Table 8-2 Assessment Schedule, Safety Follow-up

Period ¹	Post-Treatment Follow-Up			
Visit Name	Safety Follow-up Visit 1	Safety Follow-up Visit 2		Additional Follow-up Visits ²
Visit (Month)	EOS + 3 Months	EOS + 6 Months		Every 3 months
Visit Window (Day)	±14	±14		±14
Physical Exam ⁵	S	S		S
Vital Signs (including weight)	X	X		X
Routine lab samples including urine	X	X		X
Sample for CD19+ B-cells and CD3+CD20+ T-cells	X	X		X
Total IgG, IgM levels	X	X		X
Urine Pregnancy Test ^{3,5}	S	S		S
Contraception Status ^{4,5}	S	S		S
Concomitant medications ⁶	X	X		X
Adverse Events	X	X		X

X Assessment to be recorded in the clinical database or received electronically from a vendor

¹ Visit structure given for internal programming purpose only

² As needed for the Participants requiring prolonged B-cell plasma level monitoring

³ Pregnancy test is conducted on female Participants only. Urine pregnancy tests will be conducted at all scheduled visits as indicated in [Table 8-2](#). The Participant must contact the Investigator immediately in the case of a positive test for confirmatory testing at the Investigator's discretion.

⁴ Participant's contraception status must be reviewed and documented to ensure method of contraception continues to be appropriate per protocol requirement for highly effective contraception.

⁵ Assessments captured as source data

⁶ Including corticosteroids used to treat MS relapse; any newly started MS treatment as applicable.

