- For participants who meet the criterion for 6-month confirmed disability worsening on EDSS (see [Section 10.1.5](#)) during the study, the Investigator must reassess the benefits and risks of continuing study treatment. The Investigator will also discuss the further treatment with the participant, including any other MS treatment options that may be available to the participant. The outcome of the discussion with the participant must be documented in the participant's source information

- In case the Investigator deems the benefit-risk of continuing study treatment to be unfavorable or if the participant does not wish to continue study treatment and the participant does not initiate a commercial MS disease modifying therapy, the participant will be discontinued from the study and will enter the Safety Follow-up period (Table 8-2).

If discontinuation from study treatment occurs, the Investigator should make a reasonable effort to understand the primary reason for the participant's discontinuation from study treatment and record this information.

Participants who discontinue from study treatment agree to return for the end of treatment and follow-up visits indicated in the Assessment Schedule (see Table 8-1). Participants that discontinue treatment and do not initiate a commercial MS disease modifying therapy should complete the EOS visit and move to the Safety Follow-up as per Table 8-2. If they fail to return for these assessments for unknown reasons, every effort (e.g. telephone, e-mail, letter) should be made to contact the participant/pre-designated contact as specified in Section 9.1.3. This contact should preferably be done according to the study visit schedule.

If the participant cannot or is unwilling to attend any visit(s), the site staff should maintain regular contact with the participant, or with a person pre-designated by the participant. This contact should preferably be done according to the study visit schedule for up to 6 months post last study drug administration.

After discontinuation from study treatment at a minimum, in abbreviated visits, the following data should be collected at clinic visits or via telephone/email contact:

- New / concomitant treatments
- Adverse Events / Serious Adverse Events

[figure not shown]
The Investigator must also contact the IRT to register the participant's discontinuation from study drug.

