9.3 Study completion and post-study treatment

Study completion is defined as when the last participant finishes their Study Completion visit and any repeat assessments associated with this visit have been documented and followed-up appropriately by the Investigator or, in the event of an early study termination decision, the date of that decision.

A participant is considered to have completed the study when they fulfill the following criteria:

- Participant has completed the study in its entirety according to the approved duration of the study within that country

- The participant has **not** stopped the study due to one or more of the following reasons:
 - Discontinuation of study treatment (Section 9.1.1)
 - Withdrawal of informed consent (Section 9.2)
 - Lost to follow-up (Section 9.1.3)

End of Study (EOS) visit is mandatory for all participants. For participants that complete the study, the next (and last) scheduled visit is the EOS visit and should align with the overall visit schedule. Participants will then enter the Safety Follow-up according to the assessment schedule in Table 8-2 if they do not initiate a commercial MS disease modifying therapy. Participants who prematurely discontinue study treatment will have their EOS visit as soon as possible and continue into the Safety Follow-up for 6 months according to the assessment schedule in Table 8-2 if they do not initiate a commercial MS disease modifying therapy.

The Investigator must provide follow-up medical care for all Participants who are prematurely withdrawn from the study, or must refer them for appropriate ongoing care.

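### For early discontinuers on no MS DMT, Protocol 9.3 ends Safety Follow-up at 6 months while other sections run to B-cell repletion or therapy, and 10.1.3 does not define when all-cause SAE reporting stops

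*Protocol*

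**What the plan says.** **The 6-month statement.** Protocol 9.3 says that participants who discontinue early and start no commercial MS DMT "continue into the Safety Follow-up for 6 months according to the assessment schedule in Table 8-2". Its sentence on completers gives no duration.

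**Follow-up to repletion or therapy.** The protocol summary (study design) provides for "if required every 3 month post treatment safety follow-up visits until either another therapy is initiated or B cells are repleted". Section 3 names among those who enter Safety Follow-up "participants who prematurely discontinue study drug and do not continue on any MS DMT". It then says that people who neither move to commercial ofatumumab nor switch therapy "must continue into the safety FU phase, consisting of every 3 month visits including B cell monitoring", ending at commercial ofatumumab, another therapy or repletion. SAP 1.1 has the same list of participants and the same end. Section 10.1.1 continues adverse event monitoring until repletion or a commercially available MS DMT and does not separate completers from early discontinuers.

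**Softer wording after month 6.** A later paragraph of Section 3 says of participants not repleted at the 6-month visit that "further follow up visits at a 3 monthly frequency are recommended until full repletion has occurred". Table 8-2 fixes visits at EOS+3 and EOS+6 months; its footnote 2 describes later ones as "As needed for the Participants requiring prolonged B-cell plasma level monitoring".

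**Silent on duration.** Section 8 has early discontinuers "enter the Safety Follow-up period according to the schedule in Table 8-2", and 9.1.1 says that those on no commercial MS DMT "should complete the EOS visit and move to the Safety Follow-up as per Table 8-2". The 6-month limit in 9.1.1 applies only to contact with people who cannot or will not attend visits, and it counts from the last dose.

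**Where reporting ends.** Section 10.1.3 requires every SAE, whatever its cause, to be reported up to repletion for completers, up to the start of a commercial MS DMT, or up to the end of Safety Follow-up for premature withdrawals. After that, only SAEs suspected to be related are reportable. Protocol 12.5.2 and SAP 2.1 reuse the phrase, also without a definition. SAP 2.1.1.7 gives a repletion date for completers and a DMT date, and nothing for an early discontinuer who starts no DMT.

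**The concern.** The sections give one group two different lengths of follow-up, and a reporting duty depends on which one a site uses. Section 9.3 contains the only explicit duration for early discontinuers, so a site asking when Safety Follow-up ends for 10.1.3 would naturally take 6 months from there. The same site would still owe adverse event monitoring to repletion under 10.1.1. It could then learn of an SAE in a B-cell-depleted participant, judge it unrelated, and have no duty to report it.

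The group matters. The mandatory reasons for stopping treatment in 9.1.1 include PML, active serious infection or reactivation, malignancy, hypersensitivity and severe hypoproteinemia. Participants who stopped for safety could therefore have a shorter all-cause SAE window than completers, whose window runs to repletion. Under 9.4, participants would also be handled as premature withdrawals if the sponsor ended the study early.

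**Working it through.** There is no planned figure to reproduce. The check sets the clauses side by side for one person, an early discontinuer who starts no MS DMT, and then puts nominal days on the difference.

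**Step 1. When does each clause end?**

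| Place | What it governs | End point for this person |
|---|---|---|
| Protocol 9.3 | Safety Follow-up | 6 months |
| Protocol summary | Safety Follow-up visits, if required | another therapy or repletion |
| Section 3, mandatory rule | Safety Follow-up visits | commercial ofatumumab, another therapy or repletion |
| SAP 1.1 | post-treatment follow-up | commercial ofatumumab, another therapy or repletion |
| Section 10.1.1 | adverse event monitoring | commercial MS DMT or repletion |
| Section 3, later paragraph | visits after month 6 | recommended until repletion |
| Table 8-2, footnote 2 | visits after EOS+6 | as needed |
| Sections 8 and 9.1.1 | entry to Table 8-2 | none stated |
| Section 10.1.3 | all-cause SAE reporting | end of Safety Follow-up, undefined |

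The clash is between the first row and the next four. Rows six and seven lie closer to 9.3. Row eight supports neither side.

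**Step 2. Can the clauses be reconciled?** For visits, largely yes: 6 months as a base, with later visits optional. For reporting, no. Nothing says whether an optional visit extends Safety Follow-up for the purpose of 10.1.3, and 10.1.1 remains open beyond that point on any reading.

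**Step 3. Nominal length of the gap.** Inputs are EOS at day 366 (SAP Table 2-1), and EOS+6 at day 549, EOS+9 at day 640 and visit n at day 640 + 91 × (n − 3) for n > 3 (SAP Table 2-2).

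- Length of the 9.3 period: 549 − 366 = 183 days. As a check, 6 × 30.4375 = 182.6 days.
- Still depleted and untreated until EOS+9: 640 − 549 = 91 days outside all-cause reporting.
- Until EOS+12 (visit 4): day 640 + 91 = 731, and 731 − 549 = 182 days.
- Until EOS+15 (visit 5): day 640 + 182 = 822, and 822 − 549 = 273 days.

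These days place EOS at Month 12. For an early discontinuer the same intervals count from that person's own EOS visit.

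**Step 4. What is outside the gap.** SAEs suspected to be related remain reportable after the observation period (10.1.1, 10.1.3). SAP 2.8 restricts safety analyses to data before the safety cut-off, which 2.1.1.9 puts 30 days after treatment end (30.4375 in programming), so the TEAE tables do not depend on follow-up at this distance. Post-treatment data are only listed (SAP 2.1).

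**The case against.** The best defence is that 9.3, the later paragraph of Section 3 and Table 8-2 form one plan: two fixed visits, then optional ones. Section 9.3 cites Table 8-2 in the same sentence, so it does not exclude later visits. Protocol 10.1.3 and 12.5.2 and SAP 2.1 all separate completers, who go to repletion, from premature withdrawals, who go to the end of Safety Follow-up. That repeated split could be a deliberate shorter rule, with 9.3 supplying its end point.

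Much of this stands for visit scheduling. A reader might infer that 9.3 is a lone outlier against the rest of the protocol. The documents do not support that, because Sections 8 and 9.1.1 give no duration and two other places make visits after month 6 optional. Nor do the SAP windows beyond EOS+6 show that early discontinuers were meant to attend, since those windows serve all participants.

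The defence does not settle reporting. A deliberate shorter rule would still contradict the mandatory rule in Section 3, which lists this group, and would still leave 10.1.1 running to repletion. Its end point would also still have to be inferred, because 10.1.3 does not point to 9.3.

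The objection also narrows the consequence. Under 10.1.1 each adverse event record states whether the event is serious, and Table 8-2 sends adverse events at the additional visits to the clinical database. A reader might infer that late SAEs would go unrecorded altogether. The text does not support that. What is at risk is reporting to the sponsor's safety group, within 24 hours, of SAEs not suspected to be related.

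**Conclusion.** The inconsistency is real and minor. Read literally, 9.3 lets all-cause SAE reporting stop 183 nominal days after EOS for early discontinuers who are still depleted and on no MS DMT, while 10.1.1 keeps adverse event monitoring open. The further 91, 182 or 273 days are illustrations that assume continued depletion and no new therapy. The documents give no discontinuation, repletion or SAE rate, so neither the number of participants affected nor the number of SAEs missed can be estimated.

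The effect reaches late all-cause SAE reporting and the post-treatment listings. A reader might also infer that the deaths summary is affected. SAP 2.8.1.3 covers all deaths, on and after treatment, and is not tied to the end of Safety Follow-up, so there is no basis for that. The TEAE tables and the efficacy results, including the primary MRI endpoint, do not change.

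**What to change.** 1. **Protocol 9.3:** replace the 6-month duration with *until B-cell repletion or start of a commercially available MS DMT, whichever is first, with visits per Table 8-2*.
2. **Protocol 10.1.3 and 12.5.2, and SAP 2.1:** define the end of Safety Follow-up for premature withdrawals as that same point, which matches 10.1.1.
3. **SAP 2.1.1.7:** apply the repletion end date to premature withdrawals as well as completers.
4. **Section 3:** align the sentence that only recommends visits after month 6 with the mandatory rule before it. Otherwise, state that SAE reporting continues by remote contact when later visits are not attended. Aligning the sentence is preferable, because repletion is seen only in a blood sample. If remote contact is chosen, the 6-month limit on contact in 9.1.1 needs the same extension.

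The cost is mainly wording. The later visits are already in Table 8-2 and already have windows in SAP Table 2-2, and no analysis is added. The extra work is all-cause SAE reporting after EOS+6 months for early discontinuers still depleted and untreated, plus attendance at the later visits by this group if they become mandatory.

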9.4 Early study termination by the sponsor

The study can be terminated by Novartis at any time for any reason. This may include reasons related to the benefit/ risk assessment of participating in the study, practical reasons (including slow enrollment), or for regulatory or medical reasons. In taking the decision to terminate, Novartis will always consider the participant welfare and safety. Should early termination be necessary, participants must be seen as soon as possible and treated as a prematurely withdrawn participant.

The Investigator may be informed of additional procedures to be followed in order to ensure that adequate consideration is given to the protection of the participant's interests. The Investigator or sponsor depending on the local regulation will be responsible for informing IRBs/IECs of the early termination of the trial

10 Safety monitoring and reporting

10.1 Definition of adverse events and reporting requirements

10.1.1 Adverse events

An adverse event (AE) is any untoward medical occurrence (e.g. any unfavorable and unintended sign [including abnormal laboratory findings], symptom or disease) in a participant or clinical investigation participant after providing written informed consent for participation in the study. Therefore, an AE may or may not be temporally or causally associated with the use of a medicinal (investigational) product.

In addition, all reports of intentional misuse and abuse of the product are also considered an adverse event irrespective of if a clinical event has occurred.

Novartis qualified medical personnel will be readily available to advise on trial related medical questions or problems.

The occurrence of adverse events must be sought by non-directive questioning of the participant at each visit during the study. Adverse events also may be detected when they are volunteered

by the participant during or between visits or through physical examination findings, laboratory test findings, or other assessments.

Abnormal laboratory values or test results constitute adverse event only if they fulfill at least one of the following criteria:

- they induce clinical signs or symptoms
- they are considered clinically significant
- they require therapy

Clinically significant abnormal laboratory values or test results must be identified through a review of values outside of normal ranges/clinically notable ranges, significant changes from baseline or the previous visit, or values, which are considered non-typical in participants with the underlying disease. Investigators have the responsibility for managing the safety of individual participant and identifying adverse events. Clinically notable laboratory findings are defined according to the Common Terminology Criteria for Adverse Events (CTCAE) (the most current version will be used and can be found on the following web-site: <http://ctep.cancer.gov>).

Adverse events must be recorded under the signs, symptoms, or diagnosis associated with them, accompanied by the following information (as far as possible) (if the event is serious refer to [Section 10.1.2](#)):

- The Common Toxicity Criteria (CTC) AE grade (1-4)

If CTCAE grading does not exist for an adverse event, use:

1 = mild: usually transient in nature and generally not interfering with normal activities

2 = moderate: sufficiently discomforting to interfere with normal activities

3 = severe: prevents normal activities

4 = life-threatening

- Its relationship to the study treatment.
- Its duration (start and end dates) or if the event is ongoing, an outcome of not recovered/not resolved must be reported
- Whether it constitutes a SAE (see [Section 10.1.2](#) for definition of SAE) and which seriousness criteria have been met
- Action taken regarding with study treatment

All adverse events must be treated appropriately. Treatment may include one or more of the following:

- No action taken (e.g. further observation only)
- Drug interrupted/withdrawn
- Concomitant medication or non-drug therapy given
- Participant hospitalization/participant's hospitalization prolonged (see [Section 10.1.2](#) for definition of SAE)
- Its outcome (not recovered/not resolved; recovered/resolved; recovered/resolved with sequelae; fatal; or unknown).

Conditions that were already present at the time of informed consent should be recorded in medical history of the participant.

Adverse events (including lab abnormalities that constitute AEs) should be described using a diagnosis whenever possible, rather than individual underlying signs and symptoms.

Adverse event monitoring should be continued following the last dose of study treatment until the participant starts a commercially available MS disease modifying therapy or until their B cells are repleted. Repletion is defined as a concentration > the participant's baseline value prior to starting the IV anti-CD20 mAb or > the lower limit of normal, whichever is observed first.

Once an adverse event is detected, it must be followed until its resolution or until it is judged to be permanent (e.g. continuing at the end of the study), and assessment must be made at each visit (or more frequently, if necessary) of any changes in severity, the suspected relationship to the interventions required to treat it, and the outcome.

Information about adverse drug reactions for the investigational drug (ofatumumab) can be found in the Investigator's Brochure (IB). This information will be included in the participant informed consent and should be discussed with the participant during the study as needed. Any new information regarding the safety profile of ofatumumab that is identified between IB updates will be communicated as appropriate, for example, via an Investigator Notification or an Aggregate Safety Finding. New information might require an update to the informed consent and has then to be discussed with the participant.

The Investigator must also instruct each participant to report any new adverse event (beyond the protocol observation period) that the participant, or the participant's personal physician, believes might reasonably be related to study treatment. This information must be recorded in the Investigator's source documents; however, if the AE meets the criteria of an SAE, it must be reported to Novartis.

[figure not shown]
